12.5. Reporting Adverse Events

12.5.1. Routine Reporting

For the purposes of this study, the period of observation of adverse events for each subject extends from the signing of the informed consent form until their last visit including the follow-up visit or early termination, whichever is longer.

All events reported by the subject, observed by the clinical staff (events, such as abnormal, clinically significant findings from physical examinations, ECG tracings, laboratory assessments, and vital sign measurements), or elicited by general questioning will be recorded in the Institution’s source document and reported as an adverse event and captured in the adverse events CRF. If necessary, every effort will be made to obtain an adequate follow-up of the subjects. Should any subject choose to withdraw early from the study, they will be advised of the safety precautions to be taken.

Early Termination and End of Study (EOS) visit assessments should be performed, including the following: medical history, vital signs, physical exam, safety and clinical laboratory tests, ECG, and adverse event/concomitant monitoring.

Subjects will be questioned on their health status at the beginning of each visit and before their departure from the clinical site. Open-ended questions will be asked.

Classification will be performed by System Organ Class (SOC) and Preferred Term (PT) using the Medical Dictionary for Regulatory Activities (MedDRA) with the version specified by sponsor in DMP.

In general, AEs occurring secondary to other events (e.g., clinical sequelae or a cascade of events) should be identified by their primary cause. For example, if severe vomiting is known to result in dehydration, it is sufficient to record only vomiting as SAE or AE in the CRF.

However, medically significant AEs occurring secondary to an initiating event that are separated in time should be recorded as independent events on the CRF.

12.5.2. Serious Adverse Reporting

The Investigator or any other study center personnel's knowledge will notify any SAEs including fatal or life-threatening to SK Life Science, Inc. (SKLSI) and their designee IQVIA on an SAE report form, without regard to causality, within 24 hours after becoming aware of its occurrence.

If, during follow-up, any non-serious AE worsens and eventually meets the criteria for an SAE, that AE should be recorded as a new SAE.

The initial SAE report must be as complete as possible, including details of the current illness and SAE, and an assessment of the causal relationship between the event and the investigational product. Information not available at the time of the initial report (e.g., an end date for the AE, laboratory values received after the report, or hospital discharge summary) must be documented and an updated SAE report form should be forwarded to the Sponsor and their designee IQVIA within 24 hours of new/updated information. All follow-up information must be reported as soon as the relevant information is available. The notification of all SAE's should be directed to the following Sponsor representatives ([Table 12](#) and [Table 13](#)).

Table 12: Contact Information for IQVIA

Name	IQVIA
Email	[contact]
[contact]
[contact]

Table 13: Contact Information for Sponsor Medical Monitor

Name	[name]
Email	[contact]
[contact]

Table 14: Contact Information for PRA Principal Investigator

Name	[name], CPI
Email	[contact]
[contact]
[contact]

In addition, reporting of serious adverse events should follow the procedures outlined in [Table 15](#) based on the type of SAE.

Table 15: Serious Adverse Event Reporting Requirement

Type of SAE	Reporting Time Frame	Reporting Method	Contact Details
Rash with involvement of 1 other organ system or a suspected case of DRESS	Immediate	Email ^a	
Fatal or Life-threatening	Immediate	Email ^a	
All other SAEs	Within 24 hours of awareness	Email ^a	
Urgent safety concerns requiring a Medical Monitor	As needed	Telephone	

^aThe SAE report must be used for reporting

DRESS=Drug Reaction with Eosinophilia and Systemic Symptoms; SAE=serious adverse event; SKLSI=SK Life Science, Inc.;

At the time of the initial SAE report, the investigator should provide as much of the following information as possible:

- Study identifier;

- Study site;
- Subject number;
- A description of the event;
- Date of onset;
- Current Status;
- Whether study drug was discontinued;
- The reason why the event is classified as serious;
- Investigator's assessment of the association between the event and study drug.

Any adverse event that is considered serious will be reported to the IRB by the clinical site by telephone and/or by email within 3 working days. Any unexpected fatal or life-threatening SAE will be reported to the IRB by telephone and in writing within 24 hours.

SKLSI will be responsible for evaluating the events for expedited reporting, and for reporting them to the applicable regulatory agencies.

If reports of any new and unexpected AEs become available to SKLSI during the clinical portion of this study (related or not to the present study), SKLSI must advise the clinical site, through its Principal Investigator, of those events.

12.5.3. Rash/Hypersensitivity/DRESS Syndrome

Drug-induced hypersensitivity reactions with or without multi organ involvement (allergic reactions which may be fatal) including DRESS syndrome have been seen in patients taking cenobamate. DRESS which has occurred in <1% of clinical trial participants taking cenobamate stands for Drug Reaction (or Rash) with Eosinophilia and Systemic Symptoms. This condition occurs usually in the first 8 weeks after initiation of treatment and rarely happens afterwards.

Symptoms of DRESS may include:

- Rash;
- Fever;
- Inflammation of internal organs;
- Lymphadenopathy;
- Eosinophilia;
- Thrombocytopenia.

In order to ensure patient safety, and allow early identification and rapid intervention in suspected DRESS cases, the following measures must be followed:

- Any patient who reports a rash or is observed to have a rash should be carefully evaluated for a drug hypersensitivity syndrome; the evaluation should include hematology and chemistry blood tests. If a subject reports a rash by telephone, an unscheduled visit should be performed promptly.

- At the end of their study participation, all subjects must be informed to report any rash, hypersensitivity reaction or DRESS related symptoms to the investigative site as soon as they experience it.

During Study Day 4 (prior to discharge from CRU), subjects will be provided a safety card with the following hypersensitivity information and will be instructed to carry with them at all times:

- Rash may occur and may progress to Drug Reaction with Eosinophilia and Systemic Symptoms (DRESS).
- Rash or other signs or symptoms of hypersensitivity (e.g., fever, lymphadenopathy, and swelling) may herald a serious medical event and that the patient should report any such occurrence to the investigative site immediately.
- Instructions on whom and where to call in the event a symptom arises and information that can be provided to an emergency room in the event the subject cannot reach the investigator site.
- Reminder to check skin daily for evidence of rash for the first four months of therapy

At the end of their study participation, all subjects must be informed to report any rash, hypersensitivity reaction or DRESS related symptoms to the investigative site as soon as they experience it.

In addition, please remind all patients to call your office immediately if they experience any of the following symptoms:

- Rash;
- Fever;
- Swollen lymph nodes in your neck;
- Abdominal or chest pain;
- Puffy face or ankles;
- Yellowing of skin or eyes.

Investigators will be instructed to identify local specialists in dermatology, cardiology, nephrology and hepatology who can be called upon immediately to see the patient and manage their condition if DRESS syndrome is suspected.

The SK Life Science, Inc. (SKLSI) and their designee (see SAE Contact Information in Section 12.5.2) must be notified immediately of any suspected cases of DRESS syndrome as an SAE.

13. STATISTICS

13.1. Statistical and Analytical Plans

This section presents a summary of the planned clinical pharmacology and safety analyses for this study.

Safety statistical analysis details will be provided in the Statistical Analysis Plan (SAP) for this study. Clinical pharmacology analysis details (including the definition of the PK population) will be provided in the Clinical Pharmacology Data Analysis Plan (CPAP).

The Biostatistics Department of the CRO or SKLSI will generate the SAP. The SKLSI Clinical Pharmacology Department will generate the CPAP. Both the SAP and CPAP will be finalized prior to clinical database lock. Final analyses will take place after all subjects have completed the study and all data have been entered in the clinical study database.

Any deviation from the SAP and/or CPAP will be reported in the section “Changes in Planned Analysis” in the Clinical Study Report (CSR).

Statistical analyses will be performed using appropriate statistical software, such as SAS (Version 9.4 or above). PK parameters will be calculated using Phoenix WinNonlin (Version 8.1 or above).

13.1.1. Sample Size and Power

The number of subjects to be enrolled was chosen based on practical considerations and is considered sufficient for the study objectives. No formal sample size calculation was performed.

13.1.2. Analysis Populations

- **Safety Population:** All subjects who have received one dose of cenobamate
- **PK Population:** All subjects who have received one dose of cenobamate and have sufficient quantifiable PK samples to calculate primary PK parameters appropriately. The final decision to include subjects in the PK population set took into consideration possible AEs affecting the disposition of cenobamate (e.g., vomiting or diarrhea). Reasons supporting each decision will be clearly stated in the clinical study report. A sensitivity analysis may be performed if deemed necessary to support a subject’s exclusion or inclusion.

13.1.3. Pharmacokinetic Analysis

This section will be further detailed in the CPAP.

13.1.3.1. Pharmacokinetic Parameters

The PK parameters that will be derived from the cenobamate concentration versus time profiles, where data permit, are listed in [Table 16](#).

The plasma PK parameters will be estimated using a non-compartmental approach. A linear-up, log-down approach will be used to estimate the area under the plasma concentration versus time curve, and the terminal half-life will be estimated where appropriate.

Further information on the determination of PK parameters is outlined in the Clinical Pharmacology Analysis Plan (CPAP).

Table 16: Primary Pharmacokinetic Parameters

PK Parameter	Definition
C_{\max}	Maximum plasma concentration
AUC_{last}	Area under the plasma concentration vs. time curve calculated from time zero to the last sampling point that is above the lower limit of quantification
AUC_{∞}	Area under the plasma concentration vs. time curve from time zero to the last sampling point that is above the lower limit of quantification and extrapolated to infinite time
$AUC_{\% \text{extrap}}$	Ratio of AUC_t to AUC_{∞} expressed as percentage
λ_z	Terminal rate constant
$t_{\frac{1}{2}}$	Terminal half-life
t_{\max}	Time of maximum plasma concentration
C_{last}	Concentration measured at the last time point
CL/F	Oral clearance
V_z/F	Apparent volume of distribution

Other PK parameters will be determined if deemed appropriate. Details of the PK analysis will be provided in the CPAP.

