Pharmacokinetic assessment for cenobamate in plasma

- $AUC_{\%extrap}$: Percentage of the AUC that was extrapolated
- C_{last} : Last quantifiable concentration
- $t_{1/2}$: Terminal half-life
- CL/F : Oral clearance
- λ_z : Terminal rate constant
- V_z/F : Apparent volume of distribution during terminal phase

Number of Subjects: 24

Subjects will be balanced amongst gender and ethnic groups to the extent possible. A subject who prematurely ends the study and who received treatment may be replaced. In case of discontinuation related to an adverse event, the replacement will be discussed between the Investigator and SKLSI.

Main Inclusion Criteria:

1. Male or female subjects of 18 to 50 years of age (inclusive), at the time of screening
2. Able to read, understand, sign, and date a written informed consent form (ICF) before study participation at screening
3. Agree to use effective methods of contraception as described in Section 12.1.7.8 and Section 12.1.7.9.
4. Body mass index (BMI) between 18.5 and 30.0 kg/m² (inclusive) at screening
5. Judged to be in good health on the basis of medical history, physical examination, and routine laboratory measurements (i.e., without clinically relevant pathology)
6. Electrocardiogram (ECG) (12-lead), arterial blood pressure, and heart rate within the normal range of the study center or considered not clinically significant by the Investigator.
7. Able to understand and comply with protocol requirements and instructions and likely to complete the study as planned
8. Females of non-childbearing potential (18 to 50 years of age (inclusive)), who have undergone a sterilization procedure at least 6 months prior to dosing with official documentation (e.g., bilateral tubal ligation or bilateral salpingectomy or hysterectomy), or be

postmenopausal with amenorrhea for at least 1 year prior to dosing and follicle-stimulating hormone (FSH) serum levels consistent with postmenopausal status as per Principal Investigator's judgment

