5.1.2.1. Clinical Pharmacokinetics

In humans, the pharmacokinetics (PK) of cenobamate has been studied after both single dose and multiple dosing in healthy subjects. The PK of cenobamate in plasma appears to be non-proportional after single oral doses ranging from 5 to 750 mg and multiple dosing ranging from 50 to 500 mg/day. Maximum plasma concentration of cenobamate was generally observed between 1- and 4-hours post dosing and a longer terminal half-life was observed as the cenobamate dose was increased (approximately 30 hours at 5-10 mg to approximately 76 hours at 750 mg). Steady state is generally achieved after 2 weeks of treatment with once daily dosing of cenobamate, and the accumulation of cenobamate in plasma over the 50-300 mg dose range was approximately 5-fold based on total exposure (AUC).²

Cenobamate is extensively metabolized and primarily eliminated in the urine (88% of the dose).³ The disposition of cenobamate following tablet administration is not affected by food. The intra-

subject variability of cenobamate in healthy subjects is relatively low (about 14% for C_{max} and 4-5% for AUCs). No pharmacokinetic difference was observed for cenobamate between Japanese and non-Japanese healthy subjects.

Multiple drug-drug interaction (DDI) studies were performed in healthy subjects. The coadministration of carbamazepine, divalproex and oral contraceptives did not significantly modify the PK of cenobamate whereas the coadministration of phenobarbital and phenytoin significantly decreased cenobamate plasma exposure (AUC) by approximately 15% and 28%, respectively. The coadministration of cenobamate significantly decreased carbamazepine plasma exposure (AUC) by approximately 25-35%, and increased phenobarbital and phenytoin plasma exposures (AUC) by approximately 37% and 84%, respectively. The coadministration of cenobamate with oral contraceptives did not significantly modify ethinylestradiol plasma exposure (AUC) but increased slightly the exposure to norethindrone by approximately 37% for cenobamate oral doses up to 100 mg/day.

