13.1.3.4. Summary and Presentation of PK Data and Parameters in the CSR

Individual and mean plasma concentrations at each sampling time point for cenobamate will be presented in listings and tables with descriptive summary statistics including mean, geometric mean, range, standard deviation (SD) and coefficient of variation (CV). Individual, mean and/or median concentrations per treatment group will be plotted versus time on semi-logarithmic scales.

Summary statistics of PK parameters including mean, geometric mean, median, range, SD and CV will be presented by treatment group.

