2.2 Endpoints

2.2.1 **Primary Endpoints**

PK parameters will be calculated for cenobamate from plasma data. PK endpoints will be defined in the CPAP.

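### Protocol Table 16 defines AUC%extrap as AUC_t over AUC∞; with AUC_t read as AUClast this is the observed share, the complement of the Synopsis definition

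*Protocol*

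**What the plan says.** The protocol defines AUC%extrap twice.

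- **Synopsis, Further Endpoints:** "Percentage of the AUC that was extrapolated".
- **Section 13.1.3.1, Table 16:** the ratio of AUC_t to AUC∞, "expressed as percentage".

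The symbol AUC_t has no definition. The abbreviation list (Protocol section 4, Table 2) covers AUC, AUC24h, AUC∞ and AUClast only. Within Table 16 the one truncated area is AUClast, "calculated from time zero to the last sampling point that is above the lower limit of quantification".

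No other section settles the matter. Protocol 6.3.3 and SAP 4.6.1 list the further PK endpoints without AUC%extrap. Detail is deferred to the CPAP: Protocol 13.1 states "Clinical pharmacology analysis details (including the definition of the PK population) will be provided" there, Protocol 13.1.3 says "This section will be further detailed in the CPAP", and SAP 2.2.1 says "PK endpoints will be defined in the CPAP".

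On reporting, Protocol 13.1.3.4 states: "Summary statistics of PK parameters including mean, geometric mean, median, range, SD and CV will be presented by treatment group".

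**The concern.** The name of the parameter and the Synopsis both call for the part of AUC∞ that lies beyond the last quantifiable sample. The Table 16 formula, on its natural reading, gives the part that lies before it. Both statements are current text, and the one in the statistics section is the one a programmer or the CPAP author would be likely to follow.

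AUC%extrap tells a reader how far AUC∞, a primary endpoint, rests on extrapolation rather than on measured concentrations. If Table 16 were applied literally and the CPAP did not correct it, the by-treatment summaries would show nearly all of the area as extrapolated when nearly all of it had been observed. The mistake is one of definition: the documents state no value for this parameter, so no stated figure is wrong.

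**Working it through.** **Inputs**

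- The two definitions: Protocol Synopsis and Table 16, as above.
- Half-life, for illustration only: "approximately 30 hours at 5-10 mg to approximately 76 hours at 750 mg" (Protocol 5.1.2.1). None is given for 200 mg.
- Last scheduled PK sample: 456 h (Protocol Table 4).
- Assumptions: mono-exponential decline, and the time of the last quantifiable sample. The documents give a quantification limit (0.05 µg/mL, Protocol 11.3.2) but no expected concentrations, so that time cannot be derived.

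There is no plan figure to reproduce.

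**Step 1: algebra, with no assumption about the drug**

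- Synopsis: E = 100 × (AUC∞ − AUClast)/AUC∞
- Table 16 with AUC_t = AUClast: R = 100 × AUClast/AUC∞
- Sum: E + R = 100, so R = 100 − E for every profile.

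**Step 2: other readings of AUC_t**

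Table 16 would equal E only if AUC_t were the tail area after the last sample. Nothing in the documents says so. AUC24h, the other truncated area in the abbreviation list, would not give the extrapolated share either.

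**Step 3: scale**

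Under mono-exponential decline, E = 100 × 2^(−t_last/t½).

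| Half-life (h) | Last quantifiable sample (h) | t_last/t½ | Extrapolated share E | Table 16 ratio R |
|---|---|---|---|---|
| 30 | 456 | 15.2 | 0.003% | 99.997% |
| 60 | 456 | 7.6 | 0.515% | 99.485% |
| 76 | 456 | 6.0 | 1.5625% | 98.4375% |
| 76 | 360 | 4.74 | 3.75% | 96.25% |
| 76 | 264 | 3.47 | 9.00% | 91.00% |

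**Step 4: effect on the listed summary statistics**

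- Individual values, mean and median: the true figure is 100 minus the reported one.
- SD: the same for E and for 100 − E.
- CV: the SD is divided by the wrong mean. At a mean of 1.5625% the CV is understated by a factor of 98.4375/1.5625 = 63. The true CV can be rebuilt as SD/(100 − reported mean).
- Geometric mean: subtraction does not recover it. Example with true shares of 1, 2 and 4%: the geometric mean is (1 × 2 × 4)^(1/3) = 2.00. From 99, 98 and 96 it is 97.66, and 100 − 97.66 = 2.34. The individual values are needed.

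**The case against.** The best case for leaving this alone is that nothing in the study turns on it. The formulation and food comparisons use Cmax, AUClast and AUC∞ (Protocol 13.1.3.2; SAP 4.6.2 and 4.6.3). The PK population (Protocol 13.1.2; SAP 3.2) sets no limit on the extrapolated share. The name and the Synopsis make the intent plain, and a figure near 98% labelled as extrapolated would look odd beside AUClast and AUC∞. Protocol 6.3.3 leaves the full parameter list to the CPAP, and SAP 4.6.1 refers there for the summary statistics, so Table 16 may not be the final computing rule. The illustrated sizes rest on assumptions. No information would be lost, since the CV can be rebuilt from the mean and SD and the geometric mean from individual values.

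All of this stands as a limit on the impact, but it does not reconcile the two definitions. Deferral to the CPAP leaves the protocol contradicting itself, and the CPAP need only be final before database lock, so its author could take the formula from Table 16. The sections that omit the parameter do not resolve the conflict. That a careful reader might notice or undo the inversion is no reason to specify it.

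A subscript lost in conversion of the text cannot be excluded, although the neighbouring subscripts in Table 16 are intact. Even if AUC_t were meant as the tail area, it would still be an undefined symbol in a table of definitions.

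**Conclusion.** The point holds as a minor definition error in current protocol text. With AUC_t read as AUClast, Table 16 gives exactly 100 minus the quantity defined in the Synopsis. That result is algebraic and depends only on this reading, which is the natural one. The sizes are illustrations: for half-lives of 30 to 76 h and last quantifiable samples at 264 to 456 h, the cases worked run from 0.003% shown as 99.997% to 9.0% shown as 91.0%.

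Whether a wrong figure would reach the study report depends on the CPAP, which was not available and may already be correct. The primary comparisons, the PK population and the study conclusions do not depend on it.

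**What to change.** In Table 16, replace the AUC%extrap definition with 100 × (AUC∞ − AUClast)/AUC∞ and remove the symbol AUC_t. Check that the CPAP uses the same formula, and correct it there if it does not.

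The cost is one table cell and one check of the CPAP wording. Design, sampling and analyses do not change.

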13.1.3.2. Formulation and Food Effect Analysis

An analysis of variance (ANOVA) will be used to compare suspension vs. tablet formulations and suspension under fed vs. suspension under fasted conditions. PK parameter (C_{\max} , AUC_{last} , and AUC_{∞}) values will be log-transformed for all subjects included in the PK population set and the ratio and corresponding 90% CIs for the ratio of the test (suspension or fed) vs. reference (tablet or fasted) will be compared. An absence of effect will be concluded if the 90% CIs lie within the 80% - 125% predefined boundaries.

13.1.3.3. Analysis on T_{\max}

For each subject, the Wilcoxon signed-rank test will be used to test for differences in t_{\max} .

13.1.3.4. Summary and Presentation of PK Data and Parameters in the CSR

Individual and mean plasma concentrations at each sampling time point for cenobamate will be presented in listings and tables with descriptive summary statistics including mean, geometric mean, range, standard deviation (SD) and coefficient of variation (CV). Individual, mean and/or median concentrations per treatment group will be plotted versus time on semi-logarithmic scales.

Summary statistics of PK parameters including mean, geometric mean, median, range, SD and CV will be presented by treatment group.

